This is the first study that we are aware of that will look at the use of Aeroneb system to deliver bronchodilator therapy in asthma exacerbations.

The study will provide novel data to demonstrate whether the use of Aeroneb system to deliver bronchodilator therapy is advantageous to patients with severe asthma exacerbations.

If the hypothesis is proven to be correct this will mean improved patient's outcomes in severe asthma exacerbations and potentially shorter ER stay, reduction in the hospitalization rate and cost of care.

III. Research Plan

A. Experimental design:

This is a prospective, single blinded, parallel, single center, randomized controlled clinical trial (n=68). Upon entry into the study, patients will be randomized to two groups:

Treatment group: All the bronchodilator therapies during the ER visit (albuterol and ipratropium) will be delivered via Aeroneb nebulizer system. The asthma management will be as per the adult asthma protocol in the ER.

Control group: All the bronchodilator therapies (Albuterol and ipratropium) will be delivered via small volume jet nebulizer system, which is currently the standard nebulizer device used in the emergency department at Tufts Medical Center. The asthma management will be as per the adult asthma protocol in the ER.

B. Sample size and statistical analysis(es):

Upon entry into the study patients will be randomized at a 1:1 ratio with permuted block design of 6 to one of the 2 groups. Randomization will be conducted using a computerized randomization scheme and secured in a sealed envelope for allocation.

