For a power calculation to determine the sample size, historical data was utilized from prior clinical study that examined the effect of bronchodilator (B2-agonist) treatment on the improvement of the peak flow measurement after 30 minutes of the initial bronchodilator treatment⁴. In this study, the mean PEFR improved from 27% to 39% at 30 minutes after the initial bronchodilator treatment. We hypothesize that mean PEFR of the intervention group at 30 minutes of the bronchodilator therapy will be at least 10 points higher than the control group (i.e. mean PEFR \geq 49% at 30 minutes of the initial bronchodilator therapy). Group sample sizes of 34 and 34 is required to achieve a power $> 80\%$ to reject the null hypothesis of equal means when the groups mean difference is 10.0 with a standard deviation for both groups of 14.4 and with a significance level (alpha) of 0.050 using a two-sided two-sample equal-variance t-test.

Taking into consideration the screen failures the disqualification and drop-outs, we are anticipating enrolling around 110 patients in order to have 68 patients who will complete the study objectives.

For the statistical analysis treatment evaluations will be performed on the principle of intention to treat (ITT) using the data collected from all randomized participants who completed the study procedures including the two parts of the informed consent form (ICF). Demographics and baseline characteristics of patients will be summarized for each group. Continuous variables will be reported as mean \pm standard deviation, with minimum, median, and maximum values.

Categorical variables will be reported as n and %. All statistical testing will be two-sided with alpha=0.05.

For the primary outcome, mean PEFR at 30 minutes post-bronchodilator treatment, analysis of covariance (ANCOVA) with adjustment for baseline PEFR will be utilized.

ANCOVAs with adjustment for baseline values, and incorporating repeated measures where appropriate, will be utilized for the following secondary outcomes: absolute value of PEFR (L/Min) at 30 minutes, PEFR percentage of predicted at 60 minutes and 180 minutes, FEV1 percentage of predicted as well as absolute FEV1 (L/Sec) at 30 minutes, 60 minutes and 180 minutes, Borg dyspnea score at 30 minutes, 60 minutes and 180 minutes, accessory muscle use score at 30 minutes, 60 minutes and 180 minutes, and heart rate at 30 minutes, 60 minutes and 180 minutes.

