2. Psychological risk:

There is no increased psychological risk to the study participants from the study for either arm

3. Social risk:

There is no increased social risk to the study participants from the study for either arm

4. Economic risk

There is no increased economic risk to the study participants from the study for either arm.

5. Benefit of participating in the study:

- a) Patients randomized to the intervention group may benefit from the increased bronchodilator delivery by Aeroneb system
- b) Future asthma patients may benefit from this study if Aeroneb system is proven to be more effective in treating severe asthma exacerbation

E. Specific methods and techniques used throughout the study:

1. Laboratory tests:

No additional laboratory test is required in the study.

2. Study Procedures:

-The patient presenting with acute severe asthma exacerbations to the emergency room will be screened by the PI, co-investigator or research coordinator to determine their eligibility based on the inclusion and exclusion criteria.

-The required treatment must not be delayed for a research related reason and patients will still be eligible for enrollment after receiving the treatment as long as their PEFR<50%40% of predicted and the enrollment occur within 90 minutes of the ER arrival time.

- The initial part of the consenting process will cover the essential elements of the informed consent in a concise manner to ensure timely process

-Eligible patient will be randomized using the method mentioned above to either the intervention arm or the control arm. The randomization should take place within 90 minutes of the ER arrival, however, every effort will be made to enroll the patient as soon as possible; patients will be enrolled as long as their PEFR is less than 50% 40% of predicted regardless of the number of bronchodilator treatment they received prior to the randomization.

-The assignment will be blinded to the recording investigator and the treating physician but not to the patient or the nurse or respiratory therapist who is administering the nebulization. In order to avoid any delay in administering the treatments, the sets of Aeroneb nebulizer and small volume jet nebulizer will be stored in identical boxes and will be readily available in the ER.

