In order to blind the treating physician and the recording investigator, a sign "treatment in progress" will be displayed at the outdoor of the ER room when the patient is getting the bronchodilator treatment. The nebulizer devices will be placed in the box between the bronchodilator treatment sessions. The physician and the recording investigator will be asked if possible to see the patients only when the sign is taken off the outdoor.

-Once assigned, all the bronchodilator treatments in the ER will be administered using the nebulizer device assigned to that patient.

-The Peak flow and FEV1 will be measured using Spirometer (micro I). Both values will be obtained through the same exhalation maneuver.

-Patient will be treated and managed according to the asthma ER adult protocol or as directed by the ER physician who is in charge of patient's care

-After the study procedures have been performed and the subject is determined to be in stable condition and have the capacity to make medical decisions, the investigator will approach the subject again and review all the elements of the ICF again with the subject. The collected data will be used only if the subject signs both parts of the informed consent.

-Within two weeks of the subject participation, the research team will attempt to conduct a phone interview with the subject to obtain their feedback on the study procedures and mainly on the informed consent process. The phone interview questionnaire is included in the supplement

-The research team will report to the IRB the progress of the study including the consent process after enrolling the first 10 patients.

3. Subject Timeline:

During the study several data will be recorded, most of them are standard hospital recording, which are conducted frequently. These data will be collected at baseline and at multiple points after the initial bronchodilator therapy (at 30 ± 10 minutes, 60 ± 10 minutes, at 180 ± 10 minutes and upon disposition from the ER). All recorded data are obtained through noninvasive measurements. No samples of any body component will be taken that is not part of the normal standard hospital protocols.

The results that will be collected are summarized in table 1.

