The PI, co-investigator or the research coordinator will oversee the study procedure. Normal clinical care of patients will be performed by the patient's assigned nurse, respiratory therapist and doctor in the emergency room.

b. Primary responsibility for the following activities:

i. Obtaining informed consent:

The principal investigator and the co-investigators will be responsible for obtaining the informed consent from the patients.

ii. Providing on-going information to the study sponsor and the IRB:

[name] and [name] will be responsible for providing on-going information to the study sponsor and the IRB.

iii. Maintaining participant's research records:

[name] will be responsible for maintaining the participant's research records. The records will be maintained up to 7 years as per the IRB policy.

8. Subject fees:

There will be no fees paid to subjects for the study. It is part of their emergency visit care treatment

9. Study results:

Study results will not be given to patients.

10. Procedures to protect subject confidentiality:

Patient confidentiality will be maintained under normal emergency room procedures which are in compliance with the HIPPA rules.

11. Confidentiality:

a. Certificate of Confidentiality:

Certificate of confidentiality is not relevant for this research study

b. How data will be coded, recorded, and stored to protect confidentiality:

Study participants will be allocated a study number, which will be used as a study identifier on all study forms. The study data and records will be kept locked.

c. Parties who will have access to the date, including the key to the identity code:

The study PI, [name] and research team member [name] will have access to the study data and the identity codes.

d. Parties who will have access to research records:

The study PI, [name] and research team member [name] will have access to the study data.

12. Collaboration:

This is not a collaborative study.

13. Alternatives:

Patients not participating in this study will receive usual ER care as determined by the ER.

14. How new information will be conveyed to the study subject and how it will be documented:

In the event new information is discovered about the study, a letter describing the new information will be mailed to the contact address for each subject who participated in the study.

15. Payment, including a prorated plan for payment:

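### The recording investigator is declared blinded, but keeping out during nebulisation is only an 'if possible' request, and breaches are neither recorded nor examined

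*Combined protocol and SAP*

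**What the plan says.** Experimental design (III.A) gives the label: "This is a prospective, single blinded, parallel, single center, randomized controlled clinical trial (n=68"). Study Procedures (III.E.2) says who is and is not blinded: "The assignment will be blinded to the recording investigator and the treating physician but not to the patient or the nurse or respiratory therapist" giving the nebulisation.

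The same section then describes the means:

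- The two devices are stored in identical boxes.
- A sign hangs outside the room while a treatment is running.
- Between treatments the device is out of sight: "The nebulizer devices will be placed in the box between the bronchodilator treatment sessions".
- Staying out while the sign is up is a request to both people: "The physician and the recording investigator will be asked if possible to see the patients only when the sign is taken off the outdoor".

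Personnel (III.G.7) says of study staff: "The PI, co-investigator or the research coordinator will oversee the study procedure". It does not name the recorder as a separate person. Readings are due at 30, 60 and 180 minutes, each ±10 minutes, and at disposition (III.E.3). For the analysis, III.B says: "For the primary outcome, mean PEFR at 30 minutes post-bronchodilator treatment, analysis of covariance (ANCOVA) with adjustment for baseline PEFR will be utilized".

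Table 1 has no item for whether the recorder saw or was told the device, and III.B has no analysis that uses such information.

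**The concern.** The blinding is stated without qualification, but the step that makes the sign and the box effective is optional. Both measures hide the device only from someone who stays out while it is in use. One softly worded request covers two people whose reasons for entering may differ: the physician is responsible for care, while the recorder is there to take study measurements.

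The outcomes are not equally exposed:

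- **Accessory muscle use (0-5)** is graded by an observer who must tell mild from moderate from vigorous activity. This is the most direct route for observer bias.
- **PEFR and FEV1** are spirometer readings, so a recorder could influence them only through instruction and encouragement. The protocol itself treats demonstrating the manoeuvre as essential, since this is its reason for enrolling English speakers only (III.G.5).
- **Borg dyspnoea** is the patient's own rating, and the patient is unblinded by design. A recorder rule does not protect it.

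The Outcomes section (III.I) states the expected direction, higher PEFR with the Aeroneb, so an aware recorder would know which arm is expected to do better. Without a record of breaches, the sponsor could not later show that the recorder was blinded when the primary outcome was measured.

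**Working it through.** **1. Statement against means (III.E.2).**

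| Element | How firm it is |
|---|---|
| Recorder and physician blinded | stated without qualification |
| Identical storage boxes, device boxed between sessions | stated as procedure |
| Door sign during treatment | stated as procedure |
| Recorder stays out while the sign is up | request, 'if possible' |
| Patient, nurse, therapist do not disclose the device | not addressed |
| Breach recorded | no item in Table 1 |
| Breach examined in analysis | nothing in III.B |

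A recorder can therefore become aware of the device by sight or by being told. Either can happen with the plan followed as written, and neither leaves a trace.

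**2. The plan's own figure.** Inputs from III.B: difference 10 points, SD 14.4, two-sided alpha 0.05, equal-variance t-test, 34 per group.

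- SE = 14.4 × √(2/34) = 3.49; df = 66; critical t = 1.997.
- Noncentrality = 10 / 3.49 = 2.86.
- Exact power = 80.5% at 34 per group (79.3% at 33). The stated 34 per group for power above 80% is reproduced.

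**3. What an assumed bias would do.** The documents give no figure for bias, so this step is illustrative. Set the true difference to zero and let the observed difference be shifted by b points on average. The rejection rate is P(|T| > 1.997), with T noncentral t on 66 df and noncentrality b / 3.49.

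| Assumed average shift b (PEFR points) | b / SE | Two-sided error |
|---|---|---|
| 0 | 0 | 5.0% |
| 0.4 | 0.11 | about 5.1% |
| 1 | 0.29 | 5.9% |
| 2 | 0.57 | 8.7% |
| 3 | 0.86 | 13.5% |

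The average shift is the share of readings made by an aware recorder times the shift per such reading. If 20% of readings were affected by 2 points each, b = 0.2 × 2 = 0.4. To reach b = 2 at 20%, each affected reading would have to move by 2 / 0.2 = 10 points, which is the whole target effect.

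The calculation uses the unadjusted SD. The planned ANCOVA adjusts for baseline. At an assumed baseline correlation of 0.5, the residual SD is 14.4 × √(1 − 0.25) = 12.5, and shifts of 1, 2 and 3 points give 6.2%, 10.0% and 16.5%.

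**4. Cost of leaving flagged readings out.** By the same unadjusted t-test, power for 10 points is 80.5% at 34 per arm, 76.7% at 31 and 70.7% at 27.

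**The case against.** The strongest reply is that the blinding is layered and that 'if possible' is a realistic concession in an emergency department. Most of this stands.

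- A reader might infer that the request to stay out is the only blinding the outcomes have, or that III.E.2 contradicts itself. It does neither. The boxes and the sign are real measures, and the later text explains how the earlier statement is to be achieved. The gap is between an unqualified claim and a qualified, unrecorded safeguard.
- A reader might infer that the concession is needless because the recorder has no care duty and readings always fit between treatments. The documents do not establish this. The recorder's other duties are not described. Treatment follows the ER adult asthma protocol or the ER physician's direction, and no nebulisation schedule is given. The background notes that the adapter allows continuous as well as intermittent nebulisation. A treatment could run through the 20-40 minute window, and an absolute ban on entry could then cost the primary reading. That matters because III.B confines the analysis to randomised participants who completed the study procedures.
- A recorder rule does not reach the unblinded patient's own effort or Borg rating, nor does it stop anyone naming the device.
- Leaving out flagged readings selects on an event after randomisation. That event may be linked to severity, since sicker patients may be treated more often.

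These points limit the claim and shape the fix. They do not remove the gap: no breach would be recorded or examined, and the accessory muscle score is directly exposed.

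**Conclusion.** The concern holds as a low-severity design point. The plan asserts recorder blinding but does not require the recorder to stay out during nebulisation, and has no way to show afterwards whether the blinding held. The accessory muscle score is exposed directly, and PEFR and FEV1 through coaching.

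The size cannot be determined from the documents. The range of about 5.1% to 13.5% rests on an assumed average shift of 0.4 to 3 points, no true effect, 34 per arm, SD 14.4 and no baseline adjustment. At the low end the effect is negligible. A reader might infer from the upper figures that the trial's error rate is inflated, or that the trial was in effect unblinded. Neither follows: the documents show an avoidable risk, and do not show that bias occurred.

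**What to change.** In III.E.2, separate the two people and add a record:

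1. Keep the 'if possible' wording for the treating physician.
2. Require the recording investigator not to enter while the sign is up, and to take readings within the ±10-minute window with the device in its box.
3. If a treatment runs through the whole window, take the reading anyway and flag it, so that it is not lost.
4. Ask the patient, nurse and respiratory therapist not to disclose the device to the recorder.
5. Add one case-report field per reading: recorder aware of device before this reading (seen or told), yes/no.
6. In III.B, keep the full ANCOVA as primary. Repeat it without flagged readings, labelled as a sensitivity analysis only.

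The cost is a few sentences and one tick-box, with no extra staff. Some readings will move by a few minutes within their window. The sensitivity analysis has less power (for example 76.7% at 31 per arm, unadjusted) and selects on a post-randomisation event, so it cannot replace the primary result. Two exposures remain: the Borg score and patient effort, because the patient is unblinded, and outcomes that the treating physician can influence (hospitalisation, length of stay, total doses), because the physician's wording is unchanged.

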3.1 Baseline readings

Once patient is enrolled in the study, baseline characteristics such as gender, age, height, weight, BMI and race will be collected, as well as smoking history and past medical history including prior ER visits for asthma exacerbations, prior intubation for asthma exacerbation and the use of any respiratory therapy at home will be investigated and data will be collected. Clinical data such as respiratory and heart rate, blood pressure, O₂ sat and FIO₂ will be recorded. Peak flow and FEV1 will be measured by spirometer micro I during the same exhalation maneuver and they will be recorded.

The dyspnea will be graded with Borg score⁹ as outlined in figure 1 and the accessory respiratory muscle¹⁰ use will be graded as outlined in figure 2. Cough will be recorded as present or absent.

0	No difficulty	Score 0 – 6: Moderate respiratory distress
1		
2		
3		
4		
5		
6		
7		
8		Score 7 – 10: Severe respiratory distress
9		
10	Very, very hard	

Fig. 1 Borg Scale to assess Dyspnea

0	No visible tonic or phasic use of neck muscles
1	Neck muscles taut but with no respiratory modulation (i.e., tonic activity)
2	Mild respiratory modulation in neck muscle contraction
3	Moderate phasic activity (no supraclavicular or intercostal indrawing)
4	Vigorous phasic activity with indrawing
5	Vigorous phasic activity with abdominal paradox

Fig. 2 Accessory muscle use

Baseline readings upon enrolment	Routine test	Study test
Gender	•	
Age	•	
Height		•
Weight		•
BMI		•
Race		•
Smoking history (Number of pack years)	•	
Respiratory medications (home medication list)	•	
History of prior intubation for asthma exacerbation		•
Number of hospitalization for asthma exacerbations in the last year		•
Bronchodilator treatment in the EMT		•
Respiratory rate	•	
Heart rate	•	
Systolic/diastolic blood pressure	•	
O2 sat	•	
FIO2	•	
Dyspnea score		•
Cough		•
Respiratory accessory muscle use		•

Peak flow (percentage from predicted)	•	
Peak flow (L/Min)	•	
FEV1 (percent of predicted)		•
FEV1 (Liter)		•
At (30±10) minutes after nebulizer treatment		
Respiratory rate	•	
Heart rate	•	
Systolic/diastolic blood pressure	•	
O2 sat	•	
FIO2	•	
Dyspnea score		•
Cough		•
Respiratory accessory muscle use		•
Peak flow (percentage from predicted)	•	
Peak flow (L/Min)	•	
FEV1 (percent of predicted)		•
FEV1 (Liter)		•
At (60±10) minutes after nebulizer treatment		
Respiratory rate	•	
Heart rate	•	
Systolic/diastolic blood pressure	•	
O2 sat	•	
FIO2	•	
Dyspnea score		•
Cough		•
Respiratory accessory muscle use		•
Peak flow (percentage from predicted)	•	
Peak flow (L/Min)	•	
FEV1 (percent of predicted)		•
FEV1 (Liter)		•
At (180±10) minutes after nebulizer treatment		
Respiratory rate	•	
Heart rate	•	
Systolic/diastolic blood pressure	•	
O2 sat	•	
FIO2	•	
Dyspnea score		•
Cough		•
Respiratory accessory muscle use		•
Peak flow (percentage from predicted)	•	
Peak flow (L/Min)	•	
FEV1 (percent of predicted)		•
FEV1 (Liter)		•
Upon disposition from the ER		
Disposition (Home, floor or ICU)		•
Length of stay in the ER (from ER arrival time to disposition order placement time)		•
Intubation in the ER (Yes or No)		•
Need for NIV ventilation		•
Number of total albuterol treatment during the ER stay		•
Total accumulative dose of albuterol during the ER stay		•
Number of total ipratropium treatment during the ER stay		•
Total accumulative dose of ipratropium during the ER stay		•
Total dose of steroid (prednisone equivalent in mg)		•

Table 1

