3.3 Upon disposition from the ER
The following data will be collected: the disposition location (home, floor or ICU), length of stay in the ER (from ER arrival time to the disposition order placement time), intubation in the ER, need for NIV ventilation, number and total doses of albuterol treatments in the ER and number and total doses of ipratropium in the ER.

F. Assessment of Subject Safety and Development of a Data and Safety Monitoring Plan

1. Definition of Serious Adverse Event (SAE) and Adverse Event (AE) for this study:
For the purposes of this study a SAE is a serious adverse event that is life-threatening or results in death, hospitalization or prolonged hospitalization, significant disability/incapacitation, congenital anomaly or birth defects, or may jeopardize the subject's health and may require medical or surgical intervention to prevent one of the other listed outcomes. A SAE does not necessarily have to have a causal relationship with the study treatment. SAE may not be uncommon in the study due to the acute nature of patients presenting with severe asthma exacerbations that may be enrolled into the study. The study will be conducted in the emergency room, which provides a high level of monitoring and is capable of managing SAE in this acute patient group. It is possible that the Aeroneb group patients may experience more frequent side effects related to potentially more albuterol and ipratropium delivery and those side effects may include arrhythmia and tremor. Those side effects will be monitored closely and patients will be placed on continuous cardiac monitoring during the ER visit to capture any arrhythmia.
2. Reporting timeframe for SAEs and AEs:
SAEs will be reported to the IRB within five business days of the event occurring. The investigators will record and track any SAE or AE that might occur during the study. If a disproportionate number of events occur in either of the groups, then the study will be stopped. A "disproportionate number" is defined as one showing a statistically significant difference in SAEs and AEs occurrence after the recruitment of half the sample size (34 patients).
3. Accountability procedures as they relate to drugs, devices, and data:
The Principal Investigator [name] and the research team member [name] will be accountable for the study and interface with Aerogen, the study sponsor.
4. Data and Safety Monitoring Plan:

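### The albuterol and ipratropium dose outcomes compare ER-stay totals that can include doses given before randomisation, and no field separates those doses

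*Combined protocol and SAP*

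**What the plan says.** Four parts of the plan bear on this.

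- **What is collected.** The disposition rows of Table 1 hold, for each drug, a number of treatments and a cumulative dose, for example "Total accumulative dose of albuterol during the ER stay". Section 3.3 asks for "number and total doses of albuterol treatments in the ER and number and total doses of ipratropium in the ER". Neither splits the count at randomisation. The neighbouring Table 1 row counts length of stay from ER arrival, which supports reading the ER stay as the whole visit.
- **What may happen before randomisation.** Study Procedures (III.E.2) states "The required treatment must not be delayed for a research related reason" and "The randomization should take place within 90 minutes of the ER arrival". Patients qualify while their PEFR remains below the threshold, "regardless of the number of bronchodilator treatment they received prior to the randomization". The same section asks that enrolment be as prompt as possible and keeps both device sets to hand in the ER.
- **When the device applies.** "Once assigned, all the bronchodilator treatments in the ER will be administered using the nebulizer device assigned to that patient" (III.E.2). The jet nebulizer is the one "which is currently the standard nebulizer device used in the emergency department at Tufts Medical Center" (III.A).
- **How the doses are analysed.** III.B compares total doses by t-test or a non-parametric test such as Mann-Whitney, with no covariate. Total dose of each drug is a listed secondary outcome.

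The only baseline row in Table 1 on recent acute treatment is "Bronchodilator treatment in the EMT". On its wording this is not ER dosing, and it specifies neither a number nor a dose.

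**The concern.** The arms differ only from assignment onward. A nebulizer treatment given between arrival and randomisation cannot be a consequence of the assigned device, and in the Aeroneb arm it may well have been given by jet. If such treatments enter the totals, the dose outcomes measure the device's effect plus whatever was given earlier.

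Two things are at stake. First, the precision of the unadjusted comparison comes to depend on how variable the earlier doses are and how they relate to the later ones. Second, if the arms differ by chance in earlier ER dosing, the analyst can neither describe nor correct for it. III.B adjusts PEFR, FEV1, dyspnea, accessory muscle use and heart rate for their baseline values. Dose has no recorded counterpart to adjust for.

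**Working it through.** **The plan's own figure.** The only power calculation concerns PEFR (III.B): difference 10.0, SD 14.4, two-sided 5%, t-test. The standardised difference is 10/14.4 = 0.694. The noncentral t calculation gives 33.54, so 34 per group, with power 80.5%. The stated 34 is reproduced and is not in dispute. No such figure is given for dose.

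**Expected difference.** Write total = pre + post, split at randomisation. Allocation cannot influence pre, so its expected difference between arms is zero. The expected difference in mean total therefore equals the expected difference in mean post.

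**Precision of the unadjusted total.** The documents supply no dose inputs, so everything here is assumed. Let the SD of post be 1, the SD of pre be r, and their correlation be ρ. Then

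SD(total) = √(1 + r² + 2rρ), and standardised effect on the total = 0.694 / SD(total).

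The 0.694 is borrowed from PEFR purely as an illustration and has no link to dose. Worked cell: r = 0.5, ρ = 0 gives SD √1.25 = 1.118, effect 0.694/1.118 = 0.621, power 71.3%. With 34 per arm, the reference is 80.5% on post alone, unadjusted.

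| r | ρ = −0.5 | ρ = 0 | ρ = +0.5 |
|---|---|---|---|
| 0.1 | 84.1% | 80.2% | 76.4% |
| 0.25 | 87.9% | 78.1% | 69.2% |
| 0.5 | 90.3% | 71.3% | 56.9% |
| 1 | 80.5% | 51.4% | 37.1% |

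Power on the total can lie above or below the reference. At zero correlation the loss is 0.3 points for r = 0.1 and 2.4 points for r = 0.25.

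**Precision after adjustment.** Adjusting post for pre leaves residual variance 1 − ρ². Compared with the total,

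(1 + r² + 2rρ) − (1 − ρ²) = (r + ρ)² ≥ 0.

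So, under a linear relation, the adjusted analysis never has the larger variance. It pays only for estimating one slope (65 rather than 66 degrees of freedom). Simulated ANCOVA power (20,000 trials per cell) at ρ = −0.5, 0, +0.5 is 89.4%, 79.7%, 89.9% for r = 0.5 and 89.9%, 79.8%, 89.7% for r = 1. The near-tie is r = 0.5, ρ = −0.5, where (r + ρ)² = 0: 89.4% adjusted against 90.3% for the total.

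ANCOVA of the total adjusted for pre gives the same test as ANCOVA of post adjusted for pre. The missing item is therefore the pre-randomisation dose itself.

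**Chance imbalance.** The standard error of the difference between arms in mean pre is r√(2/34) = 0.243r, in units of the SD of post. That is 0.024 for r = 0.1 and 0.121 for r = 0.5.

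**The case against.** The strongest reply is that nothing here is an error. Whole-visit drug use is a legitimate outcome. It matches length of stay, which also starts at ER arrival, and it suits a study that hopes for shorter stays and lower cost. The comparison is unbiased, the plan claims no power for dose, and only two secondary outcomes are touched. The instruction to enrol promptly limits earlier dosing. A patient randomised before the first ER dose has a total identical to the post-randomisation dose. Doses may be skewed, as the Mann-Whitney option allows for, and the calculations above use normal theory. Time-stamped ER records might allow the split later.

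Most of this stands. It is why the ER-stay total should be kept, and why no size can be put on the gain. What it does not answer is that the plan permits earlier ER dosing without a cap and provides no field to separate it or adjust for it. The documents neither confirm nor rule out recovery from records, and they do not plan for it.

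Three stronger readings are tempting but unsupported:

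- A reader might infer that the totals always contain earlier doses. The documents permit them but do not say how often they occur.
- A reader might infer that the device effect is understated. A percentage reduction would look smaller on the total, but III.B plans no percentage comparison, and the expected absolute difference is unchanged.
- A reader might infer a definite loss of power. Even the direction depends on a correlation that the documents do not give.

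**Conclusion.** The point holds in a limited form. The dose outcomes are ER-stay totals that can include ER doses given before randomisation, and no listed field separates them. This rests on two readings: that the ER stay means the whole visit, and that the EMT row concerns care before the ER. The wording supports both.

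The consequence is not bias. The outcome can mix in doses unrelated to the device, and chance imbalance in earlier dosing cannot be adjusted for. The size is unknown, because every dose SD and correlation used above is an assumption. If few patients are treated before randomisation, the effect is small. The primary outcome, the sample size and the other secondary analyses are unaffected. This is a cheap improvement, not a correction of a mistake.

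**What to change.** In Table 1 and section 3.3, record the number and dose of albuterol and of ipratropium given in the ER before randomisation, separately from those given after.

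In III.B, make dose from randomisation onward the analysed quantity for both outcomes, adjusted for pre-randomisation ER dose, on a rank or transformed scale if doses are skewed. Report the ER-stay total as a supportive description of drug use over the whole visit, which dose from randomisation alone does not give.

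The cost is four extra fields (number and dose for two drugs), a little more recording for the coordinator, and a sentence or so in III.B. No extra patients or tests are needed, and the primary ANCOVA stays as written.
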